After consenting, participants will set up a time to download Zoom and learn how to use the platform if needed and will schedule their 4 sessions. After scheduling, participants will be sent a secure REDCap link to complete baseline questionnaires at their home or another private location and will be asked to complete these before their first session. Following completion of the baseline survey, participants will be randomized to either the experimental intervention or health education control condition. There will be 2 assessment points following the baseline: post-test (4 weeks later, upon completion of the program) and 3-month follow-up (3 months following post-test).

The Toolkit for Optimal Recovery after concussion (TOR-C) program, adapted during Aim 2 of the study, focuses on addressing mind-body skills that elicit the relaxation response (e.g., body scan, deep breathing, mindfulness), cognitive-behavioral strategies (e.g., reframing), acceptance and commitment skills (e.g., acceptances), and skills for returning to activity (e.g., goal setting, activity pacing). Participants randomly assigned to this intervention condition will receive daily text reminders to practice program skills as well as record their skills practice via methods such as Twilio if they consent to receive text reminders. A health education program will serve as the control condition for this aim of the study and will teach participants about health topics such as sleep, nutrition, and exercise. Participants randomly assigned to this control condition will not be assigned homework and will not receive daily text reminders. All participants (regardless of randomization) that consent to text messages, may receive text reminders for sessions and/or assessments (disseminated through EZ Texting).

The following measures will be administered at all timepoints unless otherwise stated:

Demographics (baseline only)

Credibility and Expectancy Questionnaire (baseline only)
Post-Concussion Symptom Scale
General Anxiety Disorder (GAD-7)
Hospital Anxiety and Depression Scale (HADS)
WHO Disability Assessment Scale (WHODAS) 2.0 (12-item version validated for mTBI)
Fear Avoidance Behavior after Traumatic Brain Injury (FAB-TBI)
Pain Catastrophizing Scale (PCS)
Cognitive and Affective Mindfulness Scale (CAMS-R)
Behavioral Response to Illness (BRIQ; limiting behavior and all or nothing behavior subscales)
Client Satisfaction Questionnaire (post-test only)
Medication Change (post-test only)

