Collecting identifiable information carries the risk of loss of confidentiality. However, we will take numerous steps to minimize this risk. Study data will be maintained in a locked filing cabinet and on password protected computers on Partners encrypted SFAs. Interviews will not become part of the patient's medical record and will not contain medical record numbers or names. Hardcopies of study related data and forms will be stored in a lockable file cabinet. Patient information will remain confidential by keeping identifying information (name, medical record number, and subject number) in a separate locked file cabinet. Only the investigators and

study staff specified on the consent form will have access to this information. Prior to the audio-recorded interview, participants will be instated not to share identifiable information, and if they do, it will be omitted by study staff in the transcription process.

8. Benefits

Participants may improve their ability to cope with pain and improve their mood, pain, and disability. Information gained through this study may lead to a better understanding the importance of delivery method of mind body interventions. All participants in this study will be offered the information from the 4-session Toolkit for Optimal Recovery after Concussion program, if they aren't randomized to that condition.

9. Statistical Analysis

Frequency and proportions will be used to assess feasibility of recruitment and retention procedures. Proportions of patients with scores over the midpoint on the Client Satisfaction Questionnaire and the Credibility and Expectancy Questionnaire will be used to assess satisfaction and credibility of both conditions.

10. Monitoring and Quality Assurance

Adverse Event Monitoring: Throughout the study subjects will be monitored for the occurrence of events defined as any undesirable experience or unanticipated risk. Lack of effect of treatment is not considered an event. All adverse events will be reported on an adverse event form. The Principle Investigator has the responsibility of reporting serious adverse events (death, life threatening illness or injury, serious injury, or permanent disability) to PHRC within 24-72 hours of notification.

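### Adverse events are to be monitored throughout, but no scheduled assessment asks about them: under-counting is likely, and ascertainment may differ by arm during the 4-week programme

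*Protocol*

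**What the plan says.** Protocol section 10 (Monitoring and Quality Assurance) makes a broad commitment: "Throughout the study subjects will be monitored for the occurrence of events defined as any undesirable experience or unanticipated risk". It adds that "All adverse events will be reported on an adverse event form" and that "Lack of effect of treatment is not considered an event". Serious events go "to PHRC within 24-72 hours of notification".

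Protocol section 6 (Study Procedures) sets two assessments after baseline: "post-test (4 weeks later, upon completion of the program) and 3-month follow-up (3 months following post-test"). It introduces the itemised list with "The following measures will be administered at all timepoints unless otherwise stated". The item nearest to a safety question is "Medication Change (post-test only"), so it is absent at 3 months.

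On contact, section 6 gives TOR-C participants who agree to texts a daily practice prompt and a way to log practice. For the other arm, "Participants randomly assigned to this control condition will not be assigned homework and will not receive daily text reminders".

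The SAP describes no summary of adverse events. Its by-arm reporting concerns the feasibility benchmarks.

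**The concern.** A form records events that staff already know about; it does not find them. If no scheduled contact asks, the count depends on who chooses to speak up. The time limit for serious events has the same weakness, because it runs from notification and an event that nobody mentions never starts it.

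The stake is modest but real. The deliverables in section 2 include a refined protocol to carry into an efficacy trial. If this pilot reports no adverse events, a reader could not tell whether none occurred or nobody asked, and the same untested procedure would pass to the larger trial. A second risk is that the two arms have different occasions to mention an event while the programme runs.

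**Working it through.** The plan gives no adverse-event figure to reproduce, so the check sets the sections side by side. Simple arithmetic is used only where it applies.

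**1. What is collected, and when (Protocol section 6)**

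| Listed items | Baseline | Post-test | 3 months |
|---|---|---|---|
| 8 symptom, function and coping scales | yes | yes | yes |
| Demographics; Credibility and Expectancy | yes | no | no |
| Client Satisfaction; Medication Change | no | yes | no |
| Adverse-event question | no | no | no |

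The list has 8 + 2 + 2 = 12 items, of which 10, 10 and 8 are given at the three time points. None asks about adverse events. No other section names an asker, a question or a recall period.

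**2. Time after the programme**

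Post-test falls at 4 weeks and the last assessment 3 months later, taken as 13 weeks. The share of follow-up after post-test is 13 / (4 + 13) = 13/17 = 76%. One scheduled assessment closes that interval. This figure is the length of the interval, not the fraction of events lost.

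**3. Contact by arm (Protocol section 6)**

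| Contact | TOR-C | Control |
|---|---|---|
| Four live sessions, scheduled before randomisation | yes | yes |
| Texts about sessions or assessments, with consent | possible | possible |
| Homework | yes, by contrast with control | no |
| Daily practice texts and practice recording, with consent | yes | no |

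The documented difference is the last two rows. The protocol does not say whether staff read text replies with safety in mind, or whether the texts continue after week 4.

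**4. Do other provisions elicit events?**

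- The Post-Concussion Symptom Scale, GAD-7 and HADS are repeated at 3 months, but no rule turns a worse score into an event.
- The questionnaire checks in section 10 look for completeness and out-of-range values. They are data-quality checks.
- The procedure in section 7 responds to suicidal ideation once it is raised. It does not ask about other events.

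**5. What an empty event log would mean (illustration only)**

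Assume 25 per arm, from the SAP's N=50 split equally; the allocation ratio is not stated. With zero events recorded, the one-sided 95% upper limit on the recorded risk is 1 − 0.05^(1/25) = 11.3%. If a fraction d of affected participants is detected, the limit on the true risk is 11.3% / d:

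| Assumed d | Upper limit on true risk |
|---|---|
| 1.0 | 11.3% |
| 0.8 | 14.1% |
| 0.5 | 22.6% |
| 0.3 | 37.6% |

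The values of d are assumptions. The table shows only that an empty log cannot be interpreted when d is unknown.

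**The case against.** The best reply is that silence about method does not prove passive collection. Section 6 lists measures, and an adverse-event form need not appear in a list of questionnaires. Section 10 separately commits to monitoring, and the four sessions give participants in both arms a natural occasion to report. There are also partial safeguards: the suicidality procedure at any contact, access to the investigator and study clinician if questionnaires cause distress, and Medication Change at post-test. The pilot's aims are feasibility and acceptability, and the SAP plans no between-arm comparison of events, so no planned analysis is biased.

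Much of this stands. It limits the claim to likely under-counting, and it means that no stated result is invalidated. It does not supply a question. Staff could follow every listed assessment and never ask.

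Three stronger readings are tempting, and the documents support none of them:

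- **Staff contact is unequal, so harms will be found unequally.** The sessions apply to both arms, the extra contact in TOR-C is texts and homework, and no difference is documented after week 4.
- **Nothing is collected after week 4.** Monitoring is promised, and eight scales are repeated. What is missing is scheduled elicitation, and it is missing before week 4 as well.
- **Worsening will be left out as lack of effect.** The definition of an event in section 10 is broad enough to include worsening on its plain meaning. A clarifying sentence would help, but the text does not exclude such cases.

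**Conclusion.** The point holds in a limited form. Monitoring is promised for the whole study, yet no scheduled question puts it into effect at post-test or at 3 months, so events would be learned mainly by spontaneous report. Under-counting is likely, including over the roughly 13 of 17 weeks after the programme. A difference in ascertainment between arms is possible during the 4 weeks of TOR-C texts and homework, but it is not shown.

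The size of either effect cannot be computed, because the documents give neither an event rate nor a detection rate. A reader might assume unequal detection and derive a false difference in event rates between arms. That difference would come entirely from the assumption, since equal detection gives none.

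The conclusion rests on two readings: that the list in section 6 is the full set of scheduled assessments, and that no separate unpublished procedure asks about events. This is an inexpensive improvement worth making, not a defect that undermines the feasibility results.

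**What to change.** In Protocol section 6, add one adverse-event question to the post-test and 3-month assessments, worded identically in both arms. It should ask about any new or worsened health or emotional problem since the last assessment, with the date and any care sought. In section 10, state that the answers are transferred to the existing adverse event form. In the SAP, add a descriptive summary by arm that reports solicited events separately from volunteered ones.

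Two additions are optional:

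- State in section 10 that lack of effect means no improvement and does not cover worsening.
- Summarise worsening by arm on the GAD-7, HADS and Post-Concussion Symptom Scale, which are already collected. Keep this descriptive: some participants will score worse through ordinary variation, so a worse score alone should not be counted as an event.

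The cost is a minor amendment, about a minute of participant time at each of two existing assessments, and more minor events to log. Treatment, eligibility and sample size are unaffected.

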Live Video Mind-Body Treatment to Prevent Persistent Concussion Symptoms Following mTBI

NCT05524402

05/22/2024

Pilot RCT Primary Outcome Analysis Plan. Frequency and proportions will be used to assess feasibility of recruitment and retention procedures. Proportions of patients with scores over the midpoint on the Client Satisfaction Questionnaire and the Credibility and Expectancy Questionnaire will be used to assess satisfaction, and credibility. Participants who drop-out will be counted as not meeting applicable feasibility criteria. Benchmarks that need to be met before an efficacy trial are depicted in the table below. If these are not met, revisions will be necessary. Benchmarks will be reported separately for TOR-C and HE-C. These benchmarks were previously used in NCCIH funded studies by the primary mentor (e.g. #3R34AT009356).

Power analyses. This trial is primarily focused on feasibility and acceptability, not statistical significance of efficacy. With a sample size of N=50 and assuming conservatively that the 8 feasibility criteria I will evaluate (see Section 4.9.3, below) are independent, the study will have 80% power to confirm feasibility all criteria if the expected rate of each criterion is at least 83%. Of note, we achieved 100% retention we achieved in some of our other studies, including the TOR study (preliminary study 1), and greater than 80% retention in our previous mind-body studies collected using live video. Importantly, this power analysis is not calculated to detect group differences or significant changes in outcome measures, but rather to establish feasibility. The proposed sample size is consistent with prior similar pilot trials funded by NCCIH, including a grant awarded to my primary mentor (#3R34AT009356).

Exploratory analyses: In line with common guidelines for feasibility studies, I do not aim to test efficacy of the TORC. I will focus our quantitative analyses on descriptive statistics for each quantitative measure, estimates of variance components, within-group pre-post comparisons using paired t-tests, calculation of Cohen's d effect sizes (ES) to gauge for signals for improvement in TOR-C, and exploratory correlations (e.g. between changes in anxiety and post-concussion symptoms).

Sex as a biological variable: I will assess both biological sex and gender in order to identify and account for potential sex and gender-based effects.

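### Does the 80% power to meet all 8 feasibility criteria at N=50 fail because the benchmarks are reported by arm?

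*SAP*

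**What the plan says.** The SAP's primary outcome paragraph makes the benchmarks a gate: "Benchmarks that need to be met before an efficacy trial are depicted in the table below", and revisions follow if they are not met. It then says "Benchmarks will be reported separately for TOR-C and HE-C" and, on drop-out, "Participants who drop-out will be counted as not meeting applicable feasibility criteria".

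The power paragraph begins "With a sample size of N=50 and assuming conservatively that the 8 feasibility criteria I will evaluate" and concludes that "the study will have 80% power to confirm feasibility all criteria if the expected rate of each criterion is at least 83" per cent. It refers the reader to a Section 4.9.3 for the criteria. It also says that the calculation serves to establish feasibility, not to detect group differences.

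Protocol section 9 (Statistical Analysis) adds that the satisfaction and credibility proportions "will be used to assess satisfaction and credibility of both conditions". On allocation, Protocol section 6 (Study Procedures) says only: "Following completion of the baseline survey, participants will be randomized to either the experimental intervention or health education control condition". No ratio is given.

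The benchmark table and Section 4.9.3 are not in the available text, so the pass marks, the denominators and any pass rule set out there cannot be read.

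**The concern.** The power statement names the whole-trial sample size, while the quantities that gate the next trial are to be shown by arm. If the decision is also made by arm, each criterion is judged on roughly half the participants. A proportion from 25 people varies more than one from 50, so a programme with a true rate of 83% on every criterion would miss at least one benchmark more often. The implied 20% risk of needless revision would then be too low. Feasibility is the trial's main question, so an overstated chance of passing would matter to whoever reads the result.

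**Working it through.** **Inputs.** From the SAP: N=50, 8 criteria, independence, true rate 0.83, joint power 0.80. Assumed, because the documents do not give them: 1:1 allocation (25 per arm) and one common pass mark for all criteria.

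**Formula.** With pass mark k out of n, power per criterion is s = P(X ≥ k), X ~ Bin(n, 0.83). Joint power is s^8 for the pooled sample or for one arm, and s^16 if both arms must pass all 8.

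**Step 1: reproduce the stated 80%.** This cannot be done uniquely, because the pass mark is not visible.

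| Pass mark | s | s^8 | s^16 |
|---|---|---|---|
| 35/50 (70%) | 0.9930 | 0.946 | – |
| 36/50 (72%) | 0.9836 | 0.876 | – |
| 37/50 (74%) | 0.9643 | 0.7475 | – |
| 16/25 (64%) | 0.9945 | 0.957 | 0.916 |
| 17/25 (68%) | 0.9822 | 0.866 | 0.751 |
| 18/25 (72%) | 0.9505 | 0.666 | 0.444 |
| 19/25 (76%) | 0.8815 | 0.365 | 0.133 |

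No single count gives exactly 80%. If pooling is assumed, 80% lies between 36/50 and 37/50, a benchmark of about 72–74%.

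**Step 2: what follows if the 80% is pooled and the decision is by arm.** A 72% benchmark needs 18/25; a 74% benchmark needs 18.5, so 19/25. Joint power is then 66.6% or 36.5% in one arm, and 44.4% or 13.3% if both arms must pass. Recruitment precedes randomisation and cannot be split. If it is one of the 8 and stays pooled at 72%, the figures are 0.9836 × 0.9505^7 = 68.9% for one arm and 0.9836 × 0.9505^14 = 48.3% for both.

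A check without a pass mark gives the same direction. Per-criterion power is 0.80^(1/8) = 0.9725, so z = 1.919. Halving n gives 1.919/√2 = 1.357, or 0.9126 per criterion. Then 0.9126^8 = 0.48 and 0.9126^16 = 0.23. This check also presumes that the 80% was computed at n = 50.

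**Step 3: test that presumption.** Solve for the true rate that gives exactly 80% joint power, and compare it with the SAP's 83%.

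| Calculation | True rate for 80% |
|---|---|
| Pooled, 36/50, 8 criteria | 81.9% |
| Pooled, 37/50, 8 criteria | 83.6% |
| One arm, 17/25, 8 criteria | 81.7% |
| Both arms, 17/25, 7 criteria each (pooled recruitment factor left out) | 83.3% |
| Both arms, 17/25, 8 criteria each | 83.7% |

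The by-arm rows come as close to 83% as the pooled rows. The 72–74% benchmark used in Step 2 is therefore a consequence of assuming pooling, not evidence for it.

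**Step 4: sensitivity of the by-arm figures.** With two arm-specific criteria at 72%, 0.9836^6 × 0.9505^2 = 81.8% in one arm, which is no shortfall, and 0.9836^6 × 0.9505^4 = 73.9% in both. Now suppose drop-outs fail all 8 criteria together and each rate stays at 83%. At 18/25 in TOR-C alone, power is 87.4%, 79.0% and 72.5% for retention of 85%, 90% and 95%. By-arm results thus run from 13.3% to well above 80%, depending on choices the available text does not fix.

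**The case for a change.** The best argument for a change is that the rule decides the trial's main conclusion, that the SAP puts the gate and the by-arm reporting in the same paragraph, and that one sentence would settle it before anyone sees results. Under the most literal reading of the power paragraph (50 participants, 8 tests) combined with a by-arm gate, the shortfall in Step 2 is real and not small. Pass marks low enough to rescue by-arm power, up to 17/25 for one arm or 16/25 for both, would give a pooled power of about 98% or more, which does not match a pooled 80%.

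Two parts of this stand: the arithmetic is right, and the deciding denominator cannot be read from the available text. The inference does not. The mismatch of low pass marks with a pooled 80% is no evidence against them if the calculation was by arm from the start. The SAP says the benchmarks are reported by arm, not that each arm must pass. The SAP points to a benchmark table and to Section 4.9.3, and a pass rule for each criterion would naturally sit there, so its absence from the plan cannot be asserted.

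**Conclusion.** The concern does not hold as an error in the power statement. A shortfall needs three things together: an 80% computed on all 50, a go/revise decision taken by arm, and most criteria being arm-specific with largely independent results. The available text establishes none of the first three and only assumes the independence, which the SAP itself calls conservative; positive dependence raises joint power. If all hold with 1:1 allocation, power at an 83% true rate is about 67–69% in one arm at 18/25, and lower at a higher pass mark or if both arms must pass. If the decision is pooled there is no shortfall, and if the calculation was already by arm with a pass mark near 68% there is little or none.

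Little turns on the gap. This is a pilot, a missed benchmark leads to revision of procedures, and no efficacy conclusion or patient number depends on the figure. Proportions shown by arm let any reader recover the pooled value from the counts and see which arm missed. Analysts can name the denominator for each criterion when they report, so the plan needs no change.

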Institutional Review Board Intervention/Interaction Detailed Protocol

Principal Investigator: [name].

Project Title: **Toolkit for Optimal Recovery after Concussions; TOR-C**

Version Date: 5/22/2024

For Intervention/Interaction studies, submit a Detailed Protocol that includes the following sections. If information in a particular section is not applicable, omit and include the other relevant information.

1. Background and Significance

mTBIs are prevalent and costly.

Mild Traumatic Brain Injuries (mTBIs), also known as concussions, are common and costly. In the United States, there are almost 3 million emergency room visits for TBI each year – a 47% increase over the past decade – resulting in a cost exceeding \$60 billion.¹ mTBIs account for the vast majority of TBIs, with an estimated incidence of up to 600/100,000 per year. Nearly all patients report physical (e.g., headache), emotional (e.g., irritability), behavioral (e.g., insomnia) and cognitive (e.g., difficulty concentrating) symptoms in the week after an mTBI.² Although many patients make a full recovery after mTBI, a substantial portion experience persistent (e.g., chronic) symptoms that can become intractable over time. Indeed, at 3-months post injury, up to 64%³ of patients with mTBI continue to report three or more persistent symptoms, followed by little to no improvement thereafter. Thus, it is critical to provide early interventions to prevent symptom persistence.

Psychosocial factors after TBI predict symptoms persistence and disability.

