Mind-body interventions effectively treat both individual symptoms common to mTBI (e.g., insomnia,¹⁵ headache¹⁶, and fatigue¹⁶) and anxiety.¹⁷ Further, they have also been shown to reduce stigma associated with traditional mental health referrals¹⁸ and are already popular among patients with neurological concerns.¹⁹

Mind-body interventions can be effectively delivered via live video.^{20,21} Live video represents a promising avenue for delivering preventative care for individuals with acute mTBI and anxiety, who face many barriers to in-person visits such as symptom burden, the time and cost associated with travel, the decreased flexibility in scheduling, the lower access to trained providers relative to live video delivery.²² Our team has extensive experience with the development and delivery of pilot and fully powered randomized controlled trials of mind-body interventions delivered via live video.^{23,24} Most relevant to this proposal, our team has developed a brief live video mind-body treatment, the Toolkit for Optimal Recovery After Injury (TOR)²⁵ to prevent chronic pain after acute injuries in those with high anxiety and catastrophic thinking about pain. We plan to adapt this program for the specific needs of patients with acute mTBI and anxiety, who are at risk for persistent post concussive symptoms (Toolkit for Optimal Recovery after Concussion; TOR-C).

Young adults are an optimal target for this proposal for 4 main reasons. First, sports-related injuries, a main cause of mTBI,^{26,27} are particularly common among individuals aged 24 or younger.^{28,29,30} Second, the rates of anxiety are also high (~ 40%) among this age-group, even in

the absence of an injury.³¹ Third, this population is particularly vulnerable to adverse effects on functioning following prolonged mTBI symptoms due to the demands of young adulthood as well as the neural plasticity and ongoing brain development associated with this age.³² Fourth, college-age individuals prefer live video conferencing over in-person interventions.³³ Finally, our team has access to this specific population of mTBI patients.

2. Specific Aims and Objectives

Aim: Conduct a randomized controlled trial (N=Up to 55) of the TOR-C versus a control health education program (HEP). We will use this information to determine if the TOR-C is effective in preventing chronic pain and improving anxiety in college-age individuals with acute mTBI and comorbid anxiety compared to the control program.

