Deliverables: 1) Refined protocol of patient recruitment, study protocol, and fidelity materials, and 2) ability to meet feasibility, acceptability, appropriateness and fidelity benchmarks in preparation for a future efficacy randomized controlled trial (RCT).

3. General Description of Study Design

Design and methodology are informed by the Obesity Related Behavioral Intervention Trials (ORBIT) and National Center for Complementary and Integrative Health (NCCIH) models of intervention development, which emphasize the importance of iteratively optimizing interventions to establish feasibility markers before efficacy testing.

4. Subject Selection

We will aim to maximize the inclusion of racial and ethnic minorities within the study. The MGH Sports Concussion Clinic draws patients from a wide geographical region, including urban Boston, surrounding communities, and the entire New England area. The recruited sample from MGH will resemble the patient population at MGH (2016 statistics) in its ethnic composition (70% white, 12% Hispanic; 10% black; 6% Asian, 14% native Hawaiian/pacific islander, American Indian/Alaska-Native, or others). We developed strategies to ensure recruitment of racial and ethnic minority samples using recommendations from Ibrahim & Sidani, 2014. Such strategies include: 1) training study staff in culturally sensitive communication and recruitment strategies focused on being flexible, and building rapport; 2) providing educational information to clinicians at the MGH Sports Concussion Clinic about the pivotal role of diverse opinions from diverse individuals; 3) prioritizing approaching every racial and ethnic minority patient presenting to the MGH Sports Concussion Clinic. Our team has successfully increased the recruitment of minority patients in our MGH studies using this methodology. The goal will be to ensure that patients of all racial and ethnic backgrounds feel that they are part of a community that aims to improve quality of care for concussion patients.

Inclusion/Exclusion Criteria

Inclusion Criteria

1. Diagnosed with mTBI with onset 3-10 weeks earlier (confirmed by clinic staff)
2. Clinically significant anxiety symptoms (score ≥ 5 on GAD-7 anxiety scale)³⁴
3. Age 18-35

4. English fluency and literacy
5. Ability and willingness to answer questionnaires and participate in a 4-session intervention
6. Cleared for participation by clinic/study staff

Exclusion Criteria

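### The SAP looks for a TOR-C signal in within-group change and an undefined Cohen's d, and plans no between-arm estimate of any clinical outcome

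*SAP*

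**What the plan says.** Protocol Section 6 states that "participants will be randomized to either the experimental intervention or health education control condition". It lists the outcome scales without restricting them to one arm, with a post-test at 4 weeks and a follow-up 3 months after that. Protocol Section 2 says the trial will determine whether TOR-C "is effective in preventing chronic pain and improving anxiety in college-age individuals with acute mTBI and comorbid anxiety compared to the control program".

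Protocol Section 9 covers only feasibility, satisfaction and credibility proportions. Clinical outcomes are analysed only under the SAP's exploratory analyses. That paragraph says "I do not aim to test efficacy of the TORC" and then lists descriptive statistics, variance components, "within-group pre-post comparisons using paired t-tests", a Cohen's d "to gauge for signals for improvement in TOR-C", and exploratory correlations. The SAP promises by-arm reporting for the feasibility benchmarks, but it specifies no comparison of the arms on any clinical scale. For d it states no contrast, standardiser, time point or confidence interval.

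**The concern.** Change from baseline within one arm is the sum of any treatment effect, background recovery and regression to the mean. The protocol makes the last two plausible. Section 1 says that "many patients make a full recovery after mTBI". Section 4 enrols people 3 to 10 weeks after injury and requires a GAD-7 score of at least 5, and GAD-7 is also an outcome. Randomisation to a control is the design feature that removes both influences, and the plan does not use it for clinical outcomes.

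The paired tests are not restricted to TOR-C, but running one in each arm does not help. A significant result in one arm and a non-significant result in the other is not a comparison of the two.

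The risk is that improvement in TOR-C is carried forward as a treatment signal when it is only what the control arm also shows. In addition, no analysis stated in the SAP clearly addresses the comparative aim in Protocol Section 2.

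**Working it through.** The plan gives no figure of its own on this point. Its 80% power statement concerns the feasibility criteria only. The check asks what the planned tests would show if TOR-C had no effect.

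**Inputs from the documents.** N = 50 (SAP), N up to 55 (Protocol Section 2), and retention above 80% in earlier live-video studies (SAP).

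**Assumptions.** 1:1 allocation, which is not stated, so 25 per arm; also 20 per arm (80% of 50, divided by 2) and 27 per arm (55/2, rounded down). Two-sided 5% level. The same background improvement in both arms, expressed as dz = mean change / SD of change, at 0.3, 0.5 or 0.8. Correlation between baseline and outcome r = 0.6 for the adjusted interval.

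**Step 1: probability that the TOR-C paired test is significant with zero treatment effect.** The test statistic follows a noncentral t with n − 1 degrees of freedom and noncentrality dz × √n. At n = 25 the noncentrality is 1.5, 2.5 or 4.0 and the critical value is 2.064.

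| n per arm | dz 0.3 | dz 0.5 | dz 0.8 |
|---|---|---|---|
| 20 | 0.247 | 0.565 | 0.924 |
| 25 | 0.302 | 0.670 | 0.970 |
| 27 | 0.324 | 0.706 | 0.979 |

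With smaller background change at n = 25, the probability is 0.077 for dz 0.1 and 0.16 for dz 0.2. If the shared improvement is instead fixed at 0.5 SD of the outcome, then dz = 0.5/√(2(1 − r)), and the probability at n = 25 runs from 0.59 (r = 0.4) to 0.87 (r = 0.7).

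**Step 2: probability that TOR-C is significant and the control is not.** With independent arms and the same dz this is p(1 − p). At n = 25:

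- dz 0.3: 0.302 × 0.698 = 0.211
- dz 0.5: 0.670 × 0.330 = 0.221
- dz 0.8: 0.970 × 0.030 = 0.029

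**Step 3: precision of the between-arm difference, in outcome SD units.** The unadjusted 95% CI half-width is t(0.975, 2n − 2) × √(2/n). The baseline-adjusted half-width is t(0.975, 2n − 3) × √(2/n) × √(1 − r²), where √(1 − 0.36) = 0.8.

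| n per arm | Unadjusted | Adjusted |
|---|---|---|
| 20 | 2.024 × 0.316 = 0.640 | 2.026 × 0.316 × 0.8 = 0.513 |
| 25 | 2.011 × 0.283 = 0.569 | 2.012 × 0.283 × 0.8 = 0.455 |
| 27 | 2.007 × 0.272 = 0.546 | 2.008 × 0.272 × 0.8 = 0.437 |

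**Step 4: simulation.** In 20,000 trials with 25 per arm, r = 0.6, zero treatment effect and shared dz of 0.3, 0.5 or 0.8, the paired test was significant in 0.305, 0.671 and 0.970. The mean ANCOVA difference was −0.002, 0.000 and 0.002 SD, with a mean half-width of 0.457 to 0.458 SD. The near-zero means are expected by construction; they show only that shared change cancels in the between-arm contrast.

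**The case against.** The strongest reply is that nothing is decided on these analyses. The SAP labels them exploratory, disclaims efficacy testing, and says the power calculation is not for group differences. Progression rests on the feasibility benchmarks, which are also the deliverables in Protocol Section 2. On that view the aim is a badly worded sentence, and rewording it removes the conflict. This stands in part: omitting a powered between-arm test is defensible in a pilot, and the primary feasibility conclusions are untouched. It does not cover a plan that disclaims efficacy and, in the same paragraph, runs inferential paired tests and seeks a signal for TOR-C.

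A second reply is that an undefined d could be meant as a between-arm d. That is possible, although a within-arm reading is more natural. If so, the SAP needs to say so, and much of the repair is one clause.

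A third concerns the size. The assumed background changes come from no passage, and smaller ones give smaller percentages. The protocol sentence on recovery goes on to say that a substantial portion have persistent symptoms, with up to 64% reporting three or more at 3 months and little improvement after that. Those limits are fair. But post-test falls roughly 7 to 14 weeks after injury (3 to 10 weeks plus 4), largely before or around that plateau, so some background recovery remains plausible. Regression to the mean on GAD-7 does not depend on recovery.

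Finally, between-arm intervals can also mislead by chance. With 8 repeated instruments at 2 time points, 16 independent 95% intervals would include at least one excluding zero with probability 1 − 0.95^16 = 0.56 under no effect, and less often if they are correlated. This is a reason to name outcomes and time points in advance, not a reason to prefer within-arm change.

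**Conclusion.** The concern holds and the plan should be changed. The SAP's stated signal measures are paired within-group tests and a d with no defined contrast, and neither document specifies a between-arm clinical estimate. With no treatment effect and 25 per arm, the TOR-C paired test would be significant in 30%, 67% or 97% of trials for shared dz of 0.3, 0.5 or 0.8. If both arms were tested, 21%, 22% or 3% of trials would show TOR-C significant and the control not. The percentages depend on the assumed background change, equal allocation and the 5% level. The paired-test figures are correct rejections of no change, not error rates. The structural point depends on none of these assumptions: within-arm change cannot distinguish treatment from what would have happened anyway.

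**What to change.** - Add to the SAP, as the exploratory signal estimate, the TOR-C minus control difference adjusted for the baseline value, by ANCOVA or by a mixed model using all available data from randomised participants. Name the outcomes and time points.
- Report it with a 95% CI and a standardised effect size defined on that contrast, stating the standardiser. Label it as estimation, not an efficacy test.
- Keep within-arm change as description for both arms, and state that neither it nor a within-arm d is evidence of a treatment signal.
- Reconcile the aim in Protocol Section 2 with the SAP's statement that efficacy is not tested.

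The cost is SAP wording and one sentence of the protocol aim; the data are already being collected. The downside is a wide interval, with a half-width of roughly 0.44 to 0.64 SD across the cases above. The estimate is therefore also too imprecise to size the next trial by itself, and the SAP should say so.
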